Appendix: Imputation overview and details (page 14)

ABBREVIATIONS

AUC	Area under the curve
AUSDRISK	The Australian type 2 diabetes risk assessment tool
BMI	Body mass index
CGM	Continuous glucose monitoring
CP	Current best practice
DSMC	Data safety monitoring committee
HbA1c	Glycated haemoglobin
iAUC	Incremental area under the curve
M0, M4, M12	M0 = baseline; M4 = 4 month; and M12 = 12 month assessments
SAP	Statistical analysis plan
TRE	Time restricted eating
T2DM	Type II diabetes mellitus
WOW	Study: What Or When to eat to reduce the risk of type 2 diabetes

PREFACE

This statistical analysis plan (SAP) describes the planned analyses and reporting for the WOW study to compare the impact of time restricted eating (TRE) versus current best practice (CP) in adults at high risk of 2 diabetes. The purpose of this SAP is to outline the considerations and the pre-specified analyses for the WOW study.

The project is funded by the Medical Research Future Fund Preventative and Public Health Grant MRF1200555 awarded to [name].

This study has been approved by the Central Adelaide Local Health Network Human Research Ethics Committee (#14023).

Study Objectives

Primary

To determine whether TRE is not inferior to current practice guidelines (CP) in dietetics to reduce HbA1c at 4 months, in individuals at high risk of developing T2DM.

Secondary

Secondary aim of this study is to assess the short (4 month) and long term (12 month) effect of TRE on HbA1c and glucose metabolism.

Exploratory

The exploratory aims of this study are to assess:

- Adherence of TRE vs CP over 4 and 12 months.
- The impact of TRE vs CP at 4 and 12 months on cardio-metabolic health.
- The impact of TRE vs CP at 4 months on 24-h profiles of glycaemia by CGM

Study Outcomes

Primary objective: 4 months

Primary efficacy outcome: Change in glycated haemoglobin (HbA1c)

Secondary efficacy outcomes

- Change in fasting glucose, insulin, and HOMA-IR
- Nocturnal glucose CGM AUC (midnight to 4 am)

Secondary objective: 12 months

Secondary efficacy outcomes

- Change in HbA1c
- Change in fasting glucose concentrations, insulin concentrations, HOMA-IR

Exploratory objective: Adherence

- Adherence: Self-reported (Assessed: Month 0.5, 1, 2, 3, 3.5, 4, 8, 11.5, 12)
- Diet records (energy, macronutrient intake) by diary (Assessed M0, M4, M12)
- Meal timing / eating window by self-reported meal timing, time stamped food photos (Assessed M0, M4, M12)

Exploratory objective: Cardiometabolic

- Cardiometabolic outcomes: C-reactive protein concentrations, blood lipid concentrations, blood pressure, heart rate (Assessed: M0, M4, M12)
- Liver health outcomes: Change in ALT, AST (Assessed: M0, M4, M12)
- Body mass and body composition by DXA, Waist and hip circumferences (Assessed: M0, M4, M12).
- Physical activity and sleep by inclinometer (ActivPAL), sleep assessed by questionnaire (Assessed: M0, M4, M12)
- Chronotype: by MEQ-SA (Assessed M0, M4, M12)

Exploratory objective: CGM measures

[figure not shown]
- 1) Change in 24-h profiles of glycaemia (i.e., iAUC, time-in range, glucose variability) by CGM (FreeStyle Libre Pro), (Assessed: M0, M4)

(Visit notation: M0 = baseline; M4 = 4 months; and M12 = 12 months.)

Study Details

Study Design: WOW is a parallel, single-blinded, multi-centre randomised controlled clinical trial.

Figure 1: Schedule of assessments

Study Population

Inclusion criteria

Study participants will be aged 35 to 70 years, overweight or obese (BMI: ≥ 25 but < 45 kg/m²) and will score ≥ 15 on the AUSDRISK assessment tool.

Exclusion criteria

- Type 1 or type 2 diabetes, or diabetes detected at screening HbA1c $\geq 6.5\%$ (48 mmol/mol).
- The following medical conditions: Major psychiatric disorders (schizophrenia, major depressive disorder, bipolar disorder, eating disorders)
- Gastrointestinal disorders/disease (including malabsorption)
- Haematological disorders (i.e. thalassemia, iron-deficiency anaemia)
- Insomnia
- Currently receiving, or have received treatment/diagnosis of cancer in the past 3 years (excluding non-melanoma skin cancer)
- Significant liver or kidney disease requiring ongoing medical care
- Previous or planned gastro-intestinal surgery (including bariatric surgery)
- Congestive heart failure (NYHA stage 2 or above)
- Previous myocardial infarction or significant cardiac event ≤ 6 months prior to screening
- Previous cerebrovascular event ≤ 12 months prior to screening, and/or any other condition deemed unstable by the study physician.
- Any medication used, or known to lower blood glucose, or antidiabetic medications; diuretics or combination blood pressure medications containing a diuretic; beta-blockers; glucocorticoids; anti-epileptic medications; antipsychotic medications; Medications affecting weight, appetite or gut motility, opioid medications unless combined with paracetamol in a single formulation and used occasionally on a PRN basis
- Night shift work or individuals who work any shifts after 10 pm.
- Do not consume a regular breakfast (i.e. do not eat breakfast on an average of 5 or more days per week), and do not eat for more than 12 hours per day on an average of 5 or more days per week*
- Have an extreme or restricted pattern of eating (i.e. following an intermittent fasting diet) or already engaged in a TRE protocol
- Pregnant, planning a pregnancy or currently breastfeeding
- Those who have lost or gained $>5\%$ of body weight in the last 6 months
- Current smokers of cigarettes/marijuana/e-cigarettes/vaporisers
- Anyone unable to comprehend the study protocol or provide informed consent (i.e. due to English language or cognitive difficulties)

- Participants will not have seen a dietitian in the preceding 3 months.
- Kessler Psychological Distress Scale ≥ 30
- Eating Disorder Examination Questionnaire ≥ 2.8

Sample size considerations

In a population of individuals with pre-diabetes, the difference of 0.2% in mean HbA1c was shown to be clinically relevant (Lindström 2003). As such we take the non-inferiority margin to be 0.1% and power our study for an additional benefit of 0.1% of TRE over control (i.e. powered for 0.2% mean difference). Literature suggests that the within group standard deviation to be 0.6% in this population of people with pre-diabetes (Parker 2014; Lindström 2003). Then with $n=214$ individuals with 4 months assessments (randomized 1:1 to each intervention), there is 80% power to conclude that TRE is non-inferior to CP with a margin of 0.1% in a baseline adjusted ANCOVA when the true difference is 0.1% in favour of TRE (2-sided $\alpha=0.05$).

In planning the study we expected attrition at four months would be $<20\%$ requiring a sample size of 268. However due to slow accrual due to COVID and better than expected attrition (close to 10%) the target of $n=214$ was likely to be attained with $n=247$ randomized. Approval for this change has been obtained by the independent DSMC.

Randomization details

Stratified random length blocked randomisation by site (Adelaide or Melbourne) and baseline HbA1c ($<5.7\%$ vs ≥ 5.7 to 6.5%)

Estimand Considerations

Population

- Australian adults with obesity and at risk of diabetes (see inclusion/exclusion criteria above)

Variable

- Change from baseline in glycated haemoglobin (HbA1c) at 4 months.

Treatments

- Time restricted eating (TRE)
- Current best practice (CP)

Population Level Summary

Mean difference in HbA1c between treatment groups.

Intercurrent Events

- Discontinuation of diet for any reason (including: lifestyle, dislike of diet and non-related medical adverse events).
- Unable to attend four-month HbA1c assessment due to reasons unrelated to diet (including moving overseas or interstate).
- Drop-out of study with reason unspecified.

Intercurrent Event Strategies

- Due to the intervention being dietary modification it is assumed that efficacy outcomes are strongly tied to compliance, thereby intercurrent event strategies are defined as whether individuals were able to continue the diet or not.
- Treatment policy will be assumed for individuals with diet discontinuation by assuming zero compliance thereafter.
- Hypothetical policy will be assumed for individuals who left the study (without diet discontinuation) by imputing compliance as if they had continued with the study.
- For individuals with unspecified drop-out reason diet discontinuation (yes/no) will be imputed within treatment group, then compliance will be imputed accordingly (ie treatment or hypothetical policy).

Sensitivity Analysis: Worst case

- All individuals in the TRE group with drop-out reason unknown will be assumed that they had discontinued the diet.
- All individuals in the CP group with drop-out reason unknown will be imputed as if they had continued the diet.

Sensitivity Analysis: Complete case

- No imputation, the analysis will only include individuals with HbA1c assessed at 4 months. This analysis assumes the missing data are missing completely at random.

Statistical Considerations

Error control: For the primary outcome the difference between TRE and CP will be assessed for non-inferiority. If the non-inferiority null is rejected then superiority will be tested. Two-sided 95% confidence intervals will be reported (ie one-sided 2.5% type I error rate). No multiple test adjustments will be made for secondary and exploratory outcomes.

Analysis Sets: Analyses of efficacy outcomes at 4 and 12 months (HbA1c, fasting glucose, insulin, HOMA-IR) will include all randomized individuals via multiple imputation. This process also requires physical activity and compliance data, as such analyses of these outcomes will also include all randomized individuals. Analyses of all other (exploratory) outcomes will be complete case analyses.

Covariate adjustment: All comparisons of treatment effect will include adjustment for stratification factors (site and baseline HbA1c as a continuous variable) and for sex as it is known that men are higher risk for diabetes.

Descriptive Statistics: A CONSORT flow diagram will present the number of individuals who participated in online screening, and clinic visits 0-3 (Figure 1). Descriptive summary statistics will be reported for baseline characteristics of all individuals who were randomized.

Statistical Methods

Primary Outcome

The primary analysis of the primary outcome is a covariate adjusted linear regression of differences in HbA1c at 4 months, adjusting treatment group (TRE vs CP), baseline HbA1c (continuous), site (Adelaide vs Melbourne) and sex (male vs female).

Non-inferiority will be concluded if upper 95% confidence interval of the effect estimate of the difference between groups (TRE – CP) is less than 0.1%. If non-inferiority is concluded then superiority may also be concluded if the upper 95% confidence interval excludes a between group difference of 0%.

This analysis will be performed in all randomized individuals with individuals using multiple imputation using chained equations within treatment groups and combined using Rubin's rules. The variables used in the multiple imputation are HbA1c (M0, M4 & M12), age, sex, site, fasting glucose (M0, M4 & M12) and insulin (M0, M4 & M12) concentrations, steps per day (M0, M4 & M12), nocturnal glucose CGM AUC (M0, M4), reason for dropout (related/unrelated to diet) and average compliance (first 4 months, and 4 to 12 months). Compliance will be imputed as per the intercurrent event strategies and the average compliance calculated over each period. Imputation will use multiple chained equations (*mice* R package), details of which are presented in the Appendix.

Secondary & Exploratory Outcomes

Treatment effect for the change in HbA1c at 12 months and other outcomes required for the multiple imputation of the primary outcome (assessed at 4 and/or 12 months) will be assessed using the same methodology as for the primary outcome, i.e. generalized linear regressions with multiple imputation for missing data.

Other outcomes will be analysed using generalized linear regressions adjusting for the same covariates, however these analyses will be complete case analyses.

Safety Outcomes

Summaries, for all adverse events and for those events believed to be related to the intervention, will be reported. In both cases, if an individual has experienced the adverse event on multiple occasions, only the event with the maximum grade will be reported.

When there are at least four individuals who experience a particular adverse event, a Fisher exact test will be conducted comparing the rates of occurrence (irrespective of grade) between the two intervention groups. No adjustments for multiple testing will be performed.

REFERENCES

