## HbA1c at 4 months
library(mice)
fm. <- "lm(exp(hbA1c.log.v2) - exp(hbA1c.log.v1) ~ group + sex + state + exp(hbA1c.log.v1))"
output <- summary(pool(with(
  data = rbind(mice.fit.g0, mice.fit.g1)
  , expr = eval(parse(text=fm.))
))); output
grp.est <- output$estimate[2]
grp.est.se <- output$std.error[2]
grp.est.df <- output$df[2]
grp.est.p <- output$p.value[2]
if (grp.est.p < 0.001) grp.est.p <- '<0.001'
if (grp.est.p >= 0.01) grp.est.p <- format(round(grp.est.p, 2), nsmall=2)
if (grp.est.p < 0.01 & grp.est.p >= 0.001) grp.est.p <- format(round(grp.est.p, 3), nsmall=3)
paste(
  'ITRE - CP: '
  , format(round(grp.est, 2), nsmall=2), ' ['
  , format(round(grp.est - qt(1-0.05/2, df=grp.est.df)*grp.est.se, 2), nsmall=2), ', '
  , format(round(grp.est + qt(1-0.05/2, df=grp.est.df)*grp.est.se, 2), nsmall=2), ']; p='
  , grp.est.p, sep=' '
); rm(grp.est, grp.est.se, grp.est.df, grp.est.p, output, fm.)

```

```

#####

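### Does the non-inferiority conclusion need a supportive analysis restricted to participants who followed their diet?

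*SAP*

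**What the plan says.** Under Intercurrent Event Strategies the SAP states that "it is assumed that efficacy outcomes are strongly tied to compliance", and for that reason defines the strategies by whether a participant was able to continue the diet. For those who stopped: "Treatment policy will be assumed for individuals with diet discontinuation by assuming zero compliance thereafter". Participants who left the study without stopping the diet are imputed as if they had continued. Where the drop-out reason is unknown, diet status is imputed first.

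Two sensitivity analyses follow. In the worst case, "All individuals in the TRE group with drop-out reason unknown will be assumed that they had discontinued the diet", while their CP counterparts are treated as having continued. In the complete case, "No imputation, the analysis will only include individuals with HbA1c assessed at 4 months".

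Under Primary Outcome, the imputation variables include "average compliance (first 4 months, and 4 to 12 months"). The Appendix code for the primary analysis fits "lm(exp(hbA1c.log.v2) - exp(hbA1c.log.v1) ~ group + sex + state + exp(hbA1c.log.v1")), with no compliance term. The decision rule reads: "Non-inferiority will be concluded if upper 95% confidence interval of the effect estimate of the difference between groups" (TRE – CP) is below 0.1%. Self-reported adherence, diet records and eating window are exploratory outcomes. The SAP defines no adherer or per-protocol set and no compliance threshold.

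**The concern.** In a superiority trial, non-adherence usually works against the claim. In a non-inferiority trial it can work for it: if many people in both arms do not follow their diet, the arms look alike, and a difference near zero lies inside the margin. Many non-inferiority plans therefore add an analysis of participants who followed their treatment.

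This SAP says that efficacy depends strongly on compliance, yet uses compliance only to impute missing data and as a separate exploratory outcome. Neither sensitivity analysis selects on diet followed. The worst case touches only drop-outs with unknown reason, and the complete case keeps everyone with a month-4 HbA1c however well they complied. If this were a defect, TRE could be called non-inferior mainly because neither diet was followed.

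**Working it through.** **Inputs.** From Sample size considerations: margin 0.1%, true difference 0.1% in favour of TRE, SD 0.6%, 214 participants with 4-month assessments, 1:1 allocation, 80% power. From Error control: one-sided 2.5%. Two inputs are assumed because the SAP does not give them: the correlation r between baseline and 4-month HbA1c, and the share q in each arm who get no diet effect.

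**The plan's own figure.** SE = 0.6 × √(1 − r²) × √(4/n). With r = 0.5 and n = 214, SE = 0.6 × 0.866 × 0.1367 = 0.0710. Power = Φ(0.2/0.0710 − 1.96) = 80.4%, matching the stated 80%. The same r gives a required total of 212, close to 214.

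**Dilution, TRE worse by exactly the margin when followed.** The true all-randomized difference is 0.1 × (1 − q), and P(non-inferiority) = Φ(0.1q/SE − 1.96).

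| q in each arm | True all-randomized difference | P(non-inferiority), r = 0.5 |
|---|---|---|
| 0 | 0.100% | 2.5% |
| 5% | 0.095% | 2.9% |
| 10% | 0.090% | 3.4% |
| 20% | 0.080% | 4.7% |

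For r from 0.3 to 0.7, the 10% row runs from 3.3% to 3.7% and the 20% row from 4.4% to 5.3%.

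**What these percentages are.** The SAP's null hypothesis is that the all-randomized difference is at least 0.1%. Only the first row meets it, and there the rate is 2.5%. In every other row the true difference is below the margin, so declaring non-inferiority is a correct decision. The values above 2.5% are power for a difference just inside the margin. They would be error rates only for a different question: whether TRE is non-inferior when both diets are followed.

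**Unequal adherence.** Assume CP lowers HbA1c by 0.2% and TRE by 0.1% when followed, so the difference is 0.2 × (1 − q_CP) − 0.1 × (1 − q_TRE).

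- q_TRE = 15%, q_CP = 5%: 0.190 − 0.085 = 0.105%, P = 2.1%. The null is true and the rate is below 2.5%.
- q_TRE = 5%, q_CP = 15%: 0.170 − 0.095 = 0.075%, P = 5.4%. The difference is inside the margin.

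**When TRE is truly better.** If the planned 0.1% benefit is read as the effect when the diet is followed (an assumption; the SAP does not say so), P = Φ((0.2 − 0.1q)/SE − 1.96) = 78.4%, 76.3% and 71.7% for q = 5%, 10% and 20%. Dilution then makes non-inferiority harder to show.

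**Size of the likely problem.** The only related figure is attrition close to 10%, for all reasons, which is not a non-adherence rate. The target of 214 "was likely to be attained with $n=247$ randomized"; 10% attrition would leave about 247 × 0.9 = 222.

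**Internal consistency.** The compliance sentence is the stated ground for splitting intercurrent events into diet stopped and diet continued. The Appendix carries this through: average compliance counts scores only up to the time of diet discontinuation and then enters the HbA1c imputation. Leaving compliance out of the regression is consistent with comparing groups as randomized; conditioning on it would change the question.

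**The case for a change.** The strongest case for the concern is that the exploratory adherence comparison could reveal poor compliance but could not show whether non-inferiority also holds among those who followed the diets. The scores are already collected and the Appendix already fixes how to average them, so one more regression would cost little. Defining it before unblinding would avoid a later choice guided by results. Sensitivity analyses belong in a SAP, so a missing protocol does not explain the omission.

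The factual part stands: no such analysis is planned, and a reader might find one informative. That does not make the plan faulty. Selecting on self-reported compliance after randomization compares differently selected people in the two arms, and a given score need not mean the same in two different diets. The subset would also be less precise: if 171 of 214 remained (80%), SE would be 0.6 × 0.866 × √(4/171) = 0.0795 and planning power 71%. As a supportive estimate with no pass/fail rule, it would decide nothing in the trial. Some of the worry is also already covered. Compliance is analysed by arm in all randomized participants, so low or unequal adherence would be visible. The worst case leans against TRE for drop-outs with unknown reason. The complete case probably removes many who stopped the diet and left.

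**Conclusion.** The concern does not hold. The SAP chooses an all-randomized comparison that keeps people who stop the diet, states why, and applies it consistently in the imputation and the model. The non-inferiority test keeps its 2.5% level for that comparison. The dilution figures (2.9% to 4.7% for 5% to 20% equal non-adherence) rest on assumed rates and on r = 0.5. They describe true differences of 0.095% to 0.080%, which lie inside the margin. The direction is not fixed either: clearly lower TRE adherence, or a true TRE benefit, works against declaring non-inferiority. An adherer analysis is a reasonable preference with real drawbacks. Its absence contradicts nothing in the SAP and changes no decision of the trial.

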Appendix

Data pre-processing

CGM baseline glucose algorithm estimated using the algorithm provided below. Nocturnal CGM iAUC calculated as the area under the curve of CGM glucose minus baseline between 12 midnight and 4am.

Total number of steps is set to missing if the number of assessment days is less than 5.

Imputation Overview

Missing data is imputed within allocated treatment group.

HbA1c, fasting glucose concentration, fasting insulin concentration and steps-per-day are imputed on log scale and back transformed for analyses on the original scale.

Log of the total steps-per-day is analysed with an offset of log of number of days assessed.

Baseline variables are used for imputing all variables.

All variables within an assessment period are used per assessment period, diet-discontinue (no vs yes), average compliance (per period) and repeated measures of each variable are also included.

For example imputing 4 month (log) HbA1c uses all baseline variables, all 4 month variables, the binary diet-discontinue variable, the four month average compliance and the 12 month (log) HbA1c variable.

All variables are imputed with predictive mean matching except the compliance and diet-discontinue variables for which ordinal and logistic regressions are used respectively.

```

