## Other Secondary outcomes will also adjust for their baseline and HbA1c at baseline
## Glucose at 4 months
library(mice)
fm. <- "lm(exp(glu.log.v2) - exp(glu.log.v1) ~ group + sex + state + exp(glu.log.v1) + exp(hba1c.log.v1))"
output <- summary(pool(with(
  data = rbind(mice.fit.g0, mice.fit.g1)
  , expr = eval(parse(text=fm.))
))); output
grp.est <- output$estimate[2]
grp.est.se <- output$std.error[2]
grp.est.df <- output$df[2]
paste(
  'iTRE - CP: '
  , format(round(grp.est, 2), nsmall=2), ' ['
  , format(round(grp.est - qt(1-0.05/2, df=grp.est.df)*grp.est.se, 2), nsmall=2), ', '
  , format(round(grp.est + qt(1-0.05/2, df=grp.est.df)*grp.est.se, 2), nsmall=2), ']'
  , sep=' '
); rm(grp.est, grp.est.se, grp.est.df, output, fm.)

rm(mice.fit.g0, mice.fit.g1, MNAR.type)
ls()

```

CGM code

```
CGM.baseline.fn <- function(y, t, threshold=1, smooth.range=4*2*3 + 1, iter=8) {

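### The complete-case exploratory outcomes are adjusted for baseline HbA1c but not for their own baseline values, which the trial collects

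*SAP*

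**What the plan says.** The SAP sets one covariate list under Covariate adjustment: "All comparisons of treatment effect will include adjustment for stratification factors (site and baseline HbA1c as a continuous variable) and for sex". The Primary Outcome section repeats it for the HbA1c model.

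Secondary & Exploratory Outcomes then splits the remaining outcomes in two. HbA1c at 12 months and the other outcomes used in the imputation "will be assessed using the same methodology as for the primary outcome, i.e. generalized linear regressions with multiple imputation for missing data". For the rest: "Other outcomes will be analysed using generalized linear regressions adjusting for the same covariates, however these analyses will be complete case analyses". Analysis Sets describes this second group as the exploratory outcomes.

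For outcomes other than HbA1c, own-baseline adjustment is stated in one place, a comment in the Appendix code under the secondary outcome examples: "Other Secondary outcomes will also adjust for their baseline and HbA1c at baseline". The model below it, for fasting glucose at 4 months, has change as the response and carries both baselines: "lm(exp(glu.log.v2) - exp(glu.log.v1) ~ group + sex + state + exp(glu.log.v1) + exp(hba1c.log.v1".

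Study Outcomes shows that most exploratory outcomes are measured at baseline. Two entries are "Cardiometabolic outcomes: C-reactive protein concentrations, blood lipid concentrations, blood pressure, heart rate (Assessed: M0, M4, M12" and "Liver health outcomes: Change in ALT, AST (Assessed: M0, M4, M12". Body mass, DXA, waist and hip, sleep, chronotype, diet records, eating window and the 24-h CGM profiles also have M0 values.

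**The concern.** An outcome's own baseline is usually its strongest predictor. The SAP uses it for the primary outcome, where the common covariate (baseline HbA1c) is also the outcome's own baseline, and for the secondary outcomes through the Appendix comment. For the exploratory outcomes the same list no longer does that job. A model for body weight would carry baseline HbA1c but not baseline weight, and no reason for the difference is given.

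Two things are at stake, both modest. The exploratory estimates lose some precision, and each keeps a shift from chance baseline imbalance that an already collected measurement would remove.

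**Working it through.** **The plan's own figure.** The only computed design figure is n=214 for the primary outcome. Its inputs, from Sample size considerations, are margin 0.1%, true difference 0.1% in favour of TRE (0.2% from the margin), SD 0.6%, 80% power and one-sided 2.5%.

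- Without baseline adjustment: 2 × (0.6 × (1.960 + 0.842) / 0.2)² ≈ 141.3, so 142 per arm and 284 in total.
- With ANCOVA the variance is multiplied by 1 − r². The SAP gives no r. At an assumed r = 0.5 this is 141.3 × 0.75 ≈ 106 per arm, or 212 in total by the normal approximation. The noncentral t distribution gives 80.02% power at 214.

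So 214 reproduces as an own-baseline analysis with r near 0.5. The present point does not depend on that figure, but it shows that the sponsor already relies on own-baseline adjustment.

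**Inputs for the exploratory outcomes.** The SAP gives neither SD nor correlation for them. Assumed: M0-to-follow-up correlation r = 0.5, 0.7 or 0.9; equal SDs at both times; 107 complete cases per arm (214 / 2); response = change from M0, as in all three coded models. Results are in units of the baseline SD. Baseline HbA1c is first taken as uncorrelated with the outcome.

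**Formulas.**

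- Residual variance without own baseline: 2(1 − r). With it: 1 − r².
- SE ratio (with / without): √((1 + r)/2).
- Participants giving the same SE with own baseline: 214 × (1 + r)/2.
- SD of the chance difference in baseline means: √(2/107) = 0.137. Its 95% range is 1.96 × 0.137 = ±0.268.
- 95% CI half-width: 0.268 × √(residual variance).
- Difference between the two estimates: (1 − r) × baseline imbalance, so its 95% range is ±0.268 × (1 − r).

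| | r = 0.5 | r = 0.7 | r = 0.9 |
|---|---|---|---|
| SE ratio | 0.866 | 0.922 | 0.975 |
| SE reduction | 13% | 8% | 3% |
| Equivalent n (instead of 214) | 161 | 182 | 203 |
| Half-width without own baseline | 0.268 | 0.208 | 0.120 |
| Half-width with own baseline | 0.232 | 0.191 | 0.117 |
| Shift removed (95% range) | ±0.134 | ±0.080 | ±0.027 |

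**Does baseline HbA1c already do the work?** Let c be its correlation with the outcome's M0 value, and let it relate to follow-up only through that value. The SE ratio becomes √((1 − r²) / (2(1 − r) − c²(1 − r)²)), and the shift is multiplied by √(1 − c²). At an assumed c = 0.3 the ratios are 0.876, 0.928 and 0.977, and the shifts ±0.128, ±0.077 and ±0.026. HbA1c recovers almost nothing.

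**Simulation.** In 8,000 simulated trials of 214 participants, with group, sex, site and baseline HbA1c in the model and c = 0, the ratios were 0.87, 0.93 and 0.97 and the shifts ±0.14, ±0.08 and ±0.03. With a true effect of zero, both estimators averaged within 0.003 of zero.

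**The case against.** The best defence is that the covariate list is not exhaustive. It says what comparisons will include, which sets a minimum. The imputed secondary outcomes are given the primary methodology without any mention of own baseline, and the Appendix then adds it. An analyst could read the sentence on the remaining outcomes in the same spirit, or by analogy, since baseline HbA1c is the primary outcome's own baseline. It can also be said that a valid and slightly less precise exploratory model is not an error.

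Part of this stands. The SAP does not forbid own-baseline adjustment, and the Appendix comment is a general rule for secondary outcomes rather than a remark about glucose alone. But the comment names secondary outcomes in a document that separates them from exploratory ones, the list names HbA1c explicitly, and no sentence carries the rule across. If own-baseline adjustment was intended throughout, one sentence confirms it.

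It is also right that M0 is not unused where the response is change: it enters by subtraction. What is missing is M0 as a covariate. ALT/AST and the 24-h CGM profiles are worded as change. The other affected outcomes are not, so for them a change response is inferred from the coded models.

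**Conclusion.** The point holds as a minor, nearly free improvement. As written, the complete-case exploratory outcomes with an M0 value are not adjusted for it. On change scores, own-baseline adjustment would lower the SE by about 13%, 8% or 3% and remove a shift with a 95% range of about ±0.13, ±0.08 or ±0.03 baseline SD, for correlations of 0.5, 0.7 or 0.9. These figures rest on assumed correlations, equal SDs and 107 complete cases per arm. At r = 0.9 the gain is negligible.

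A reader might infer three stronger things that the document does not support:

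- **Bias.** Randomisation keeps the comparisons unbiased. Chance imbalance adds noise to a single trial's estimate but is not systematic.
- **Harm to the main results.** The primary model and HbA1c at 12 months contain their own baseline, and the Appendix rule covers the other secondary outcomes.
- **A large loss of precision.** When r exceeds 0.5, the loss would be greater if raw follow-up values were modelled without M0: the SE ratio would be √(1 − r²), which is 0.714 at r = 0.7. The SAP shows no such model.

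**What to change.** Amend Secondary & Exploratory Outcomes to state that each complete-case exploratory outcome with an M0 measurement is also adjusted for its own M0 value, in addition to site, sex and baseline HbA1c, within the generalized linear regression already planned. This extends the Appendix rule from secondary to exploratory outcomes and needs no change of model type. Self-reported adherence has no M0 value and is excluded.

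The cost is one sentence and one term per model. Where the response is change from M0, no participant is lost, because M0 is already needed. If a follow-up value is modelled instead, the few participants without M0 would drop out of that complete-case analysis.
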